3.0 STUDY PARTICIPANT SELECTION CRITERIA

3.1 Inclusion Criteria

- Participant is at least 18 years of age
- Participant presents with one or more of the following symptoms: chronic pain, anxiety, depression, and/or sleeplessness
- Participants must score greater than or equal to a 5/10 for their primary symptom score on the Baseline Symptom Questionnaire
- Patient's chosen primary symptom must have an available accrual slot for the participant. If patient scores greater than or equal to a 5/10 for a second symptom, they can be selected to accrue to another symptom slot.
- Participant has signed the Informed Consent Form

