4.0 STUDY PROTOCOL

The Nu-V3 Clinical Study is a randomized, open-label study using the Nu-V3 cranial nerve stimulation treatment device in patients with chronic pain, anxiety, depression, and/or sleeplessness. Study participants are those who have signed the informed consent form, met the inclusion and exclusion criteria, and are enrolled in the study at one of multiple sites.

Subjects randomized to receive the Nu-V3 treatment will undergo the following regimen:

- At the baseline visit, patients will be asked to complete study questionnaires (Appendix 11) regarding all of the following symptoms: chronic pain, anxiety, depression, and/or sleeplessness, as well as their quality of life, active medications, medical history, and demographical information. The subject's primary symptom of concern will also be notated at baseline, for later assessment of continuation after week 12.
- At each subsequent visit, patients will be asked to complete study questionnaires regarding all the following symptoms: chronic pain, anxiety, depression, and/or sleeplessness, as well as their activity level and quality of life.
- The sessions will begin with the Nu-V3 device being clipped on the ear and three small pads (non-invasive) adhered to the surface of the ear. Each Nu-V3 device lasts for up to 28 days with a change in the pads approximately 7 days into the treatment.
- Each session takes approximately 15-20 minutes. The placement of the device takes approximately 5 minutes, and the remaining time is spent verifying ePRO form completion, and evaluating the patient for all device effects.
- The Nu-V3 device is mobile and is worn externally on the left ear 24 hours a day during treatment, fitting comfortably behind the ear. An electrical signal is sent to

the external ear through coated wire leads attached to the device and adhesive pads which attach to three sites on the ear.

- Participants should be able to perform their typical day-to-day activities while wearing the device. They may shower while wearing the Nu-V3 device, if they do not get the device wet and use the small disposable ear covers that are provided for them.
- In the event the Nu-V3 gel pads are inadvertently removed or the device comes off, the participant will contact the site coordinator. The participant is encouraged to adjust the device placement as needed for comfort.
- Patients should not change their existing forms of treatment or medications without discussion with the study investigator.

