Subjects randomized to the observation control arm of the study will undergo the following regimen:

- At the baseline visit, patients will be asked to complete study questionnaires (Appendix 11) regarding all the following symptoms: chronic pain, anxiety, depression, and/or sleeplessness, as well as their quality of life, active medications, medical history, and demographical information. The subject's primary symptom of concern will also be notated at baseline.
- At each subsequent visit, patients will be asked to complete study questionnaires regarding all the following symptoms: chronic pain, anxiety, depression, and/or sleeplessness, as well as their activity level and quality of life.
- Patients should not change their existing forms of treatment or medications without discussion with the study investigator.
- At completion of 12 weeks of standard of care treatment post study enrollment, observation (control arm) subjects will be offered a crossover into the treatment arm of the study for an additional 24 weeks.

Sample size

For this Phase II study, a total of 100-200 subjects will be randomized 1:1 to either the Nu-V3 treatment arm or to the observation treatment arm (SOC, control).

Recruitment

Participants are enrolled into relevant symptom cohorts based on their chronic pain, anxiety, depression, and/or sleeplessness symptom presentation at baseline and treated with the Nu-V3 device for 24 weeks.

Analyses

Interim analysis of reported data will be based on baseline symptom cohort and conducted at 6, 12, 18, and 24 weeks during this time. The participant will be evaluated after the initial 12-week treatment period to assess for further therapeutic need. Upon having three consecutive weeks of mean symptom reduction of $\geq 70\%$ via patient reported numerical scales, the participant will continue as described in the study assessments table, but without device therapy. Then if the participant's primary

symptom score increases at any time by $\geq 20\%$, they may again continue device therapy until week 24, as depicted in section 4.1.

Study subjects randomized to the observation arm will be offered the opportunity to cross-over to the Nu-V3 study treatment arm upon completion of the initial 12-week observation study period.

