5.0 DATA COLLECTION AND RETENTION

The study endpoints data will be collected from each participant's study questionnaires. The data will be collected electronically via the patient's own device and uploaded to an electronic data capture system. The data will be used to measure whether the Nu-V3 device provides participants with a reduction in participants' chronic pain, anxiety, depression, and/or sleeplessness.

The data analysis will include baseline data for each participant's questionnaire prior to beginning treatment with the Nu-V3 device. Longitudinal data will consist of participant's weekly questionnaires measuring chronic pain, anxiety, depression, and sleeplessness during the treatment phase. The final data collection will be completed by participants at the end of the treatment with the Nu-V3 device and will measure chronic pain, anxiety, depression, and sleeplessness.

The Principal Investigator at each site will be responsible for recording, collecting, and storing the research participant's study data. The written records will be stored in a secure location. Only the Principal Investigator or designated study staff will have access to the study records and all electronic files will be password protected. The Principal Investigator will also maintain adequate records for the study including:

- all correspondence with the IRB and Sponsor
- other pertinent data related to the study

All records are to be retained by the Principal Investigator for a period of three (3) years following the closure of the study. Following study closure, the Principal Investigator shall inform Nu-Life of the location of study records and storage changes (i.e., the Principal Investigator leaves the institution where the study was conducted). In such cases, the study records may be transferred to another institution, investigator, or to Nu-Life upon written agreement between the Principal Investigator and Nu-Life.

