8.0 STUDY ENDPOINT and DATA ANALYSIS

8.1 Primary Endpoints: Primary endpoints consisted of the following:

Safety: At screening/baseline, a medical history will be obtained to capture relevant underlying conditions. The screening/baseline examinations will include BP, and HR. Baseline signs and symptoms are those that are assessed within 14 days prior to week 1 treatment.

Concomitant medications will be collected from within 14 days prior to enrollment through the study treatment period and maintenance period (see Study Assessments Table section 4.1).

The primary safety endpoint is the occurrence of reported unanticipated problems involving risk to subjects or others (“UPIRTSOs”). These UPIRTSOs are defined as those problems which alter the risks to subjects or others. This includes any study suspensions or holds. The primary safety endpoint analyses will be based on a risk-benefit conclusion.

Effectiveness: There are four instruments measuring participant’s symptoms of chronic pain, anxiety, depression, and sleeplessness. The primary effectiveness endpoint is a statistically significant reduction in one or more of measures of: chronic pain, anxiety, depression, or sleeplessness between baseline and 12 or 24 weeks after initiating treatment.

The null hypothesis to disprove is that there is no statistically significant reduction from baseline to 12 or 24 weeks in mean chronic pain, anxiety,

depression, or sleeplessness symptom severity scores using the Nu-V3 device compared with the usual care cohort.

The instruments used in this study are:

Chronic Pain – Pain intensity (P), interference with enjoyment of life (E), and interference with general activity (G) (PEG Scale),

The PEG is a three-item instrument that measures pain intensity (one item) and pain interference (two items). Each item is valued from 0 (no pain/interference) to 10 (as bad as you can imagine). The instrument score is calculated as the average of the three item values.

Anxiety - Generalized Anxiety Disorder 7-item (GAD-7)

The GAD-7 is a seven-item instrument that measures respondents' symptoms of anxiety. Each item is scored on a four-point Likert scale, and values range from 0 ("Not at all") to 3 ("Nearly every day".) Items are summed to determine the instrument's score. Values of 10 or higher have been associated with moderate anxiety, while values of 15 or higher have been associated with severe anxiety.

Depression - Patient Health Questionnaire (PHQ-9)

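### Section 8.1 states two inconsistent success criteria: an endpoint sentence with no comparator, which can be read as a within-arm fall from baseline, and a null hypothesis that compares the device with usual care

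*Protocol*

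**What the plan says.** Under Effectiveness, Protocol section 8.1 states: "The primary effectiveness endpoint is a statistically significant reduction in one or more of measures of: chronic pain, anxiety, depression, or sleeplessness between baseline". The sentence ends by setting the interval as "between baseline and 12 or 24 weeks after initiating treatment". It mentions neither arm.

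The paragraph that follows gives the null hypothesis. It is worded as "no statistically significant reduction from baseline to 12 or 24 weeks in mean chronic pain" (with the other three symptoms), and it ends with "symptom severity scores using the Nu-V3 device compared with the usual care cohort". This statement does name a comparator.

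The surrounding design, from the same protocol:

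- Section 4.0: "The Nu-V3 Clinical Study is a randomized, open-label study", and "a total of 100-200 subjects will be randomized 1:1" to the device or to observation under standard care.
- Section 4.0: controls are offered the device once they have completed 12 weeks. The control assessment table in section 4.1 ends at week 12.
- Section 3.1: "Participants must score greater than or equal to a 5/10 for their primary symptom score on the Baseline Symptom Questionnaire".
- Section 5.0: "The data analysis will include baseline data for each participant's questionnaire prior to beginning treatment with the Nu-V3 device". The rest of that passage describes follow-up during and at the end of device treatment and does not mention controls.

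**The concern.** The two statements in 8.1 can give opposite answers on the same data. If the device arm falls significantly from baseline and the usual-care arm falls by the same amount, the endpoint sentence taken alone is satisfied and the null hypothesis is not rejected. The protocol does not say which one decides.

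A shared fall is plausible here. Patients enter with a primary symptom rated at 5/10 or more, standard care continues in both arms, and symptoms may improve in their natural course. The randomised control arm is there to take out whatever both arms share. If the endpoint sentence governs, success could be declared without using that arm, and the report could credit the device with a change that usual care also produced.

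**Working it through.** **1. The two statements side by side**

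| | Endpoint sentence | Null hypothesis |
|---|---|---|
| Quantity | reduction from baseline | reduction from baseline |
| Times | 12 or 24 weeks, counted from initiating treatment | 12 or 24 weeks |
| Comparator | none | usual care |
| Both arms fall equally | met, if the fall is significant | not rejected |

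Elsewhere the protocol names the arms when it wants both. Section 8.2 does so for percentage change, for the PGIC and for the perceived-benefit form. The omission in 8.1 is therefore not a standing convention.

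At week 24 there is no protected concurrent control, so the only clean analysis at that time is before-and-after. The choice of 12 or 24 weeks makes the within-arm reading easier to adopt.

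**2. Inputs for the size**

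From the protocol: 100-200 patients at 1:1, so 50-100 per arm; four measures; entry at 5/10 or more. The protocol gives no alpha, SD, correlation or expected change, so there is no figure of its own to reproduce. Assumed throughout: two-sided alpha 0.05, only results in the device's favour counted, no dropout, zero device effect.

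**3. One measure at one time, with a fall *f* (in SD units) shared by both arms**

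For a paired within-arm test with baseline to follow-up correlation *r*:

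P = Φ( f·√n / √(2(1−r)) − 1.96 )

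Example with n = 50, f = 0.2, r = 0.5: 0.2 × 7.071 / 1 = 1.414; 1.414 − 1.96 = −0.546; Φ = 0.293.

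| Shared fall | n = 50, r = 0.5 to 0.7 | n = 100, r = 0.5 to 0.7 |
|---|---|---|
| 0.1 SD | 11-15% | 17-25% |
| 0.2 SD | 29-45% | 52-73% |
| 0.3 SD | 56-78% | 85-97% |

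The between-arm test of change stays at about 2.5% whatever *f* is.

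**4. Regression to the mean alone, one measure**

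Selection is on a separate 0-10 item. The expected fall is therefore (correlation of that item with baseline minus its correlation with follow-up) × the mean of the selected item in SD units. With a cut-off at the mean and correlations 0.6 and 0.5, this is 0.1 × 0.80 = 0.08 SD. With a cut-off at +0.5 SD and correlations 0.8 and 0.5, it is 0.3 × 1.14 = 0.34 SD.

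Simulation over cut-offs from −0.5 to +0.5 SD and screening correlations of 0.6-0.8 with baseline and 0.5-0.6 with follow-up (r = 0.6) gave falls of 0.05-0.34 SD. Within-arm significance was 6-79% (n = 50) or 7-98% (n = 100). Between-arm significance was 2.1-2.9%.

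**5. At least one of four measures, week 12**

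Base model: four symptoms correlated 0.4; 0-10 scale with mean 4.5 and SD 2.5; entry if the worst symptom is at least 5; entry item correlated 0.8 with the same-day state; 12-week correlation 0.5-0.85.

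| Scenario, no device effect | Within-arm, n = 50 | Within-arm, n = 100 | Between-arm |
|---|---|---|---|
| Base model | 18-32% | 22-47% | 7-9% |
| Scale mean 6 instead of 4.5 | 11-16% | 12-16% | not tabulated |
| Entry item equally correlated with baseline and week 12 | 6-10% | 6-10% | 8-10% |
| Base model plus 0.5-point shared improvement (0.5/2.5 = 0.2 SD), 12-week correlation 0.7 | 94% | over 99% | 7-8% |

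The between-arm figures exceed 2.5% because four measures are tested. For independent measures the value is 1 − 0.975⁴ = 9.6%. The same multiplicity sits inside every within-arm figure.

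**The case against.** The strongest reply is that the two statements are meant to be read together, the first naming the variable and the second the comparison. The null follows at once and is the only explicit hypothesis in the section. If it governs, a fall shared by both arms would not count as success at week 12. The protocol's own usage supports this: section 8.2 counts change from initiation in both arms, and section 4.0 calls the control an observation treatment arm, so initiating treatment need not mean starting the device.

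This stands against one inference that a reader might draw, that the primary endpoint is settled as a one-arm before-and-after test. The documents do not support that. Section 5.0 does not settle it either, since it describes data collection, sets no success rule and does not exclude control data.

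The reply does not remove the inconsistency. The protocol nowhere says that the null supplies the comparison for the endpoint sentence.

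A second objection concerns the size. The inputs are assumed. Entry uses a 0-10 item with 30-day recall, while the outcomes are PEG, GAD-7, PHQ-9 and PROMIS with one- or two-week recall. The base model also admits patients on their worst symptom, whereas the protocol uses the chosen primary symptom or, where slots require, a second one. This objection stands. Regression to the mean may be small and mainly confined to the primary-symptom instrument, so no single false-success rate should be quoted.

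**Conclusion.** Section 8.1 contains two criteria that a fall shared by both arms would separate, and no rule for choosing between them. That follows from the text alone.

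The size depends on assumptions. With no device effect, the chance of a within-arm success on at least one measure runs from about the between-arm level (under 10%) to well over 40%, and higher if both arms improve together. The upper figures require either an entry item that tracks baseline more closely than week 12, or a real shared improvement. The protocol supplies neither.

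A reader might also infer that a between-arm test would remove expectation effects. It would not: the study is open-label with a no-device control, and expectation confined to the device arm stays in the contrast. The comparison removes only what the arms share.

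**What to change.** Reword the 8.1 endpoint to match its own null hypothesis: the difference between the Nu-V3 and usual-care arms in change from baseline to week 12 in the instrument score. Add that within-arm changes from baseline are descriptive and cannot by themselves meet the primary endpoint.

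Say openly that week 24 also becomes descriptive, because controls are offered crossover after week 12 and their assessment table ends there.

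A sentence in section 5.0 saying that both arms' data are analysed would help but is optional.

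The cost is a few sentences in 8.1. No new data are needed, since both arms already complete the questionnaires at weeks 1 and 12. The downside is a harder success criterion than a fall from baseline. The rewording does not deal with open-label expectation in the device arm, nor with the rule that one or more of four measures suffices, which is a separate matter.

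### Section 8.1 lets any one of four instruments, at week 12 or 24, establish primary effectiveness, and the protocol names no primary time point and states no error control for that rule

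*Protocol*

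**What the plan says.** Protocol section 8.1 introduces the primary effectiveness endpoint with "There are four instruments measuring" the four symptoms: PEG for pain, GAD-7 for anxiety, PHQ-9 for depression and PROMIS 4a for sleeplessness. Success is defined by these words: "statistically significant reduction in one or more of measures of: chronic pain, anxiety, depression, or sleeplessness between baseline and 12 or 24 weeks", counted from the start of treatment.

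The hypothesis follows: "The null hypothesis to disprove is that there is no statistically significant reduction from baseline to 12 or 24 weeks". It again joins the four symptoms by *or*, and it ends with "compared with the usual care cohort". The endpoint sentence has no such comparator and speaks only of change from baseline.

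Neither sentence selects an instrument, a time point or an order of testing, and the protocol gives no significance level. Each participant's primary symptom is recorded at baseline (sections 3.1 and 4.0), but the endpoint is not tied to it.

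Two design facts bear on this. Section 4.0 says that "a total of 100-200 subjects will be randomized 1:1". It also says that, after 12 weeks, "observation (control arm) subjects will be offered a crossover into the treatment arm of the study for an additional 24 weeks". The control assessment table in section 4.1 ends at week 12.

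**The concern.** The protocol itself fixes the rule by which the trial succeeds, and that rule is disjunctive twice over: any of four instruments, and either of two times. If each test is run at a conventional level, the chance that at least one succeeds for an ineffective device exceeds that level. A positive primary result could then rest on one instrument at one time.

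Two wording faults add to this. A null hypothesis should be a statement about the true difference. Here it is a statement about whether a test is significant, so a significant p-value refutes it by definition. The endpoint and the null also describe different comparisons: change from baseline in one, change relative to usual care in the other.

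**Working it through.** The protocol offers no figure to reproduce. It states no significance level, sidedness, power, effect size or standard deviation.

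**Inputs from the protocol**
- Instruments: 4 (section 8.1).
- Time points: 2, weeks 12 and 24 (section 8.1).
- Direction: success requires a reduction, so only favourable results count (section 8.1).
- Sample size: 100 to 200 in total, 1:1, hence 50 to 100 per arm (section 4.0).

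**Assumptions**
- Each test compares arms at two-sided 5%, which is 2.5% in the favourable direction.
- The four instruments are equally correlated, from 0 to 0.7.
- The same instrument at weeks 12 and 24 correlates at 0.6. Different instruments at different weeks correlate at the product of the two values.

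**Four week-12 tests, no true effect, favourable direction**
- Independent: 1 − 0.975^4 = 0.096.
- Correlated, by simulation of equicorrelated normal test statistics: about 9% at 0.3, about 8% at 0.5 and 6.5% at 0.7.
- Relative to 2.5%: 9.6 / 2.5 = 3.9 times, falling to 6.5 / 2.5 = 2.6 times.

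**Adding four week-24 tests, favourable direction**
- Instruments uncorrelated: about 16%. Instruments correlated at 0.7: about 11%.
- Relative to 2.5%: 16 / 2.5 = 6.4 times, falling to 11 / 2.5 = 4.4 times.
- These treat week 24 as if it had a valid usual-care comparison. Controls are offered the device after week 12 and their table stops there, so the week-12 figures are the firmer ones.

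**Effect of an adjustment over the four week-12 tests**
- First Holm step: 0.05 / 4 = 0.0125. With independent tests, 1 − (1 − 0.0125)^4 = 0.049 in either direction, so the familywise 5% holds.
- Power for an instrument with an assumed 80% at 0.05: Φ(1.960 + 0.842 − 2.498) = Φ(0.304) = 0.62.
- Under an assumed standardised effect of 0.5, power per test at 0.05 and at 0.0125 is 70.5% and 50.1% with 50 per arm, or 94.2% and 85.0% with 100 per arm.

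**The case against.** The strongest reply is that the protocol is silent on adjustment; it does not say that the tests are unadjusted. Requiring success on at least one of several measures is a legitimate design when the error is shared among them, and the level and method are commonly left to the analysis plan. That stands. A reader might infer that the tests will be unadjusted, but the document does not show it. What remains is that section 8.1 fixes the either/or rule, leaves the time point open and misstates the null. Those sentences need correcting where they stand, whatever the analysis plan adds.

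A reader might also quote larger error rates: 1 − 0.95^4 = 18.5% for four independent tests, or 31% to 22% with both time points. Those count significant results in either direction. Section 8.1 requires a reduction, so a significant worsening cannot be a success, and the favourable-only rates apply.

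It is tempting to count eight equal tests. Only the four at week 12 have an intact randomised comparator.

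It is also tempting to object that success on one symptom would count while the other three worsen. That follows from the objective in section 2.0, relief from one or more symptoms. It is a design choice, and Holm would not remove it.

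Finally, this is an open-label Phase II study, where looser error control can be defended. But section 2.0 sets out to demonstrate the device's ability to give relief, and section 8.1 states a hypothesis to be disproved. A rule presented in those terms should have a stated error rate.

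**Conclusion.** The point holds in this form: section 8.1 declares primary effectiveness on any one of four instruments at 12 or 24 weeks, with no primary time point and no error control stated in the protocol. If the tests are between arms and each is run at two-sided 5%, an ineffective device meets the rule with probability about 9.6% to 6.5% at week 12, against 2.5% for a single test. With week 24 added it is about 16% to 11%. The level, the sidedness and all correlations are assumptions, because the protocol gives none.

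The rates apply only to the between-arm reading. If the endpoint sentence were taken literally as change from baseline within the device arm, they would not apply. Participants must score at least 5 out of 10 on their primary symptom to enter, so regression to the mean and natural course could then produce success without any device effect.

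The interim analyses at 6, 12, 18 and 24 weeks are not counted, since the protocol does not say they can decide the primary claim.

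The wording of the null does not change these rates, but it is an error in the text and should be corrected with the rest.

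**What to change.** Rewrite the effectiveness paragraph of section 8.1 to state that:
- the primary comparison is the device minus usual-care difference in change from baseline to week 12, in all randomised participants;
- effectiveness is declared on an instrument only if that difference favours the device and is significant after Holm adjustment over the four instruments, at a familywise two-sided 5%;
- week 24 results are secondary and descriptive;
- the null hypothesis, for each instrument, is that the true mean change to week 12 does not differ between arms.

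Naming all randomised participants matters because participants are enrolled into symptom cohorts, and section 8.1 does not say whether an instrument is tested in everyone or only in its cohort.

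The change is one paragraph in the protocol, carried into the analysis plan. It keeps all four symptoms and still allows a claim on any one of them. The price is power: the first Holm step needs p < 0.0125, so an assumed 80% at 0.05 becomes about 62%. Later Holm steps are less strict. At the lower end of the planned sample size the loss is material and should be weighed when the final number is chosen.

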Nu-V3 Treatment Arm Evaluation*	Week 13	Week 14	Week 15	Week 16	Week 17	Week 18	Week 19	Week 20	Week 21	Week 22	Week 23	Week 24
Medications Form ¹				x				x				x
In office assessment	x	x		x	x		x	x		x	x	x
New Device Placed ²	x			x			x			x		
Pad Replaced ²		x			x			x			x	
Treatment Forms ¹	x	x		x	x		x	x		x	x	
No Device			x			x			x			x
HRV Assessment (optional) ³	x	x		x	x		x	x		x	x	
ePRO Questionnaires ⁴	x	x	x	x	x	x	x	x	x	x	x	x
Patients' Global Impression of Change ePRO form (PGIC) ⁴	x	x	x	x	x	x	x	x	x	x	x	x
Providers' Global Impression of Change ePRO form (PGIC) ¹		x			x			x		x	x	
Optional Patient Media Testimony ⁵	x	x		x				x				x

1. Providers' PGIC form, Medications and Treatment forms to be completed by site via online module.
2. Upon having three consecutive weeks of mean symptom reduction of ≥70% via patient reported numerical scales, the participant will continue as described in the study assessments table, but without device therapy. Then if the participant's primary symptom score increases at any time by ≥20%, they may again continue device therapy until week 24.
3. (Optional) HRV assessment before the first treatment and again 15-20 minutes following the first treatment. HRV assessment will also be conducted prior to each weekly treatment. This assessment is applicable to participating sites per the clinical trial agreement. Contact the clinical trial manager for information.
4. ePRO questionnaires completed on patient's mobile device: DQ-9 (baseline), PTB-7, PEG, GAD-7, PHQ-9, PROMIS 4a, PGIC
5. If patient consents to media testimony, site will collect via study collection process.

Nu-Life Solutions Miniaturized Wearable Medical Technology - NuJ ³	Control Study Assessments Table											NuJ ³
	*Evaluations are completed weekly, every 7 days ±3 days											
Control Arm Evaluation*	Week 1	Week 2	Week 3	Week 4	Week 5	Week 6	Week 7	Week 8	Week 9	Week 10	Week 11	Week 12
Informed Consent	x											
Inclusion and Exclusion ¹	x											
Patient Registration ¹	x											
Medications Form ¹	x			x				x				x
Patient Onboarding and Orientation ²	x											
In office assessment	x			x				x				x
No Device	x	x	x	x	x	x	x	x	x	x	x	x
ePRO Questionnaires ³	x			x				x				x
Patients' Global Impression of Change ePRO form (PGIC) ³				x				x				x

1. Inclusion/Exclusion, Registration, Medications, Treatment, and Providers' PGIC forms to be completed by site via online module.

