2. Patient Onboarding and Orientation includes introductory demographics form, Nu-V3 patient training video
3. ePRO questionnaires completed on patient's mobile device: DQ-9 (baseline), PTB-7, PEG, GAD-7, PHQ-9, PROMIS 4a, PGIC

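### The primary null compares the device with usual care at 12 or 24 weeks, but no usual-care score is scheduled after week 12, so its 24-week part cannot be tested

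*Protocol*

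**What the plan says.** Section 8.1 of the protocol defines the primary effectiveness endpoint as a significant reduction in at least one of four symptom measures "between baseline and 12 or 24 weeks after initiating treatment". It then gives the null to be disproved as "no statistically significant reduction from baseline to 12 or 24 weeks in mean chronic pain, anxiety". The rest of that sentence supplies the other two symptoms and the comparator: "depression, or sleeplessness symptom severity scores using the Nu-V3 device compared with the usual care cohort". The second statement brings in the comparator, so the hypothesis is device against usual care at either time point.

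Section 4.0 sets the length of the control period. After 12 weeks of standard care, "observation (control arm) subjects will be offered a crossover into the treatment arm of the study for an additional 24 weeks". The Analyses paragraph repeats that this offer comes "upon completion of the initial 12-week observation study period". The same section plans an analysis at 24 weeks. On size, it says that "a total of 100-200 subjects will be randomized 1:1 to either the Nu-V3 treatment arm or to the observation treatment arm".

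Section 4.1 gives the visit schedules. The device arm has two tables, for weeks 1 to 12 and weeks 13 to 24. The "Control Arm Evaluation" table covers weeks 1 to 12 only. The four primary instruments reach controls through its ePRO row, whose footnote reads "ePRO questionnaires completed on patient's mobile device: DQ-9 (baseline), PTB-7, PEG, GAD-7, PHQ-9, PROMIS 4a, PGIC".

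Secondary endpoint 2 in section 8.2 asks for mean percentage change at 12 and 24 weeks in both arms, counted from a starting point that it does not define for the observation arm.

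**The concern.** A between-arm null needs data from both arms, in the state that the hypothesis names, at the time that it names. At week 24 the device side is scheduled and the usual-care side is not. Because the two time points are joined by *or*, a week-24 finding can count as success on the primary hypothesis although nothing at week 24 can test it.

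Anyone asked for the 24-week result against usual care would have to substitute something else. A within-arm change is the most likely substitute and the least safe one. The trial is open-label, the outcomes are self-reported symptoms, and section 3.1 admits only people who score at least 5 out of 10 on their primary symptom. Improvement from baseline in one arm then cannot be separated from regression to the mean or expectation, which is what a randomised control arm is there to remove.

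**Working it through.** The protocol gives no figure to reproduce on this point. The check compares the two arms' schedules.

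**Inputs**
- Control ePRO weeks (section 4.1, control table): {1, 4, 8, 12}. There is no control table after week 12.
- Device-arm ePRO weeks (section 4.1, two device tables): every week from 1 to 24.
- Crossover offered after week 12, for 24 further weeks (section 4.0).
- 100 to 200 subjects, allocated 1:1 (section 4.0).

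**Step 1. Shared assessments.** The weeks common to both schedules are {1, 4, 8, 12}, and the last is week 12. Week 24 is in the device schedule only. Weeks 13 to 24 hold 24 − 12 = 12 device-arm assessments and 0 usual-care assessments.

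**Step 2. Controls affected.** 100/2 = 50 to 200/2 = 100 controls. The number with a scheduled usual-care score at week 24 is 0 in either case.

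**Step 3. What a control could contribute after week 12.**

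| Control subject | Study week 24 | 24 weeks after device start |
|---|---|---|
| Crosses over | On the device pathway, 24 − 12 = 12 weeks after crossover | Study week 12 + 24 = 36 |
| Declines crossover | No visit scheduled | Does not apply |

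Neither row gives a usual-care value at week 24. Carrying the last usual-care value forward would set 24 weeks of device follow-up against 12 weeks of usual care.

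**Step 4. Could controls who decline fill the gap?** The protocol does not schedule them, so this is an illustration. Assume that 5% to 30% decline and are nevertheless assessed at week 24, with two-sided alpha 0.05 and 80% power (none of these figures is in the protocol). The detectable standardised difference is (1.960 + 0.842) × √(1/n₁ + 1/n₂).

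| Device arm n₁ | Controls left n₂ | Detectable difference |
|---|---|---|
| 50 | 2.5 (5%) | 2.802 × √(0.020 + 0.400) = 1.82 |
| 50 | 15 (30%) | 2.802 × √(0.020 + 0.067) = 0.82 |
| 100 | 5 (5%) | 2.802 × √(0.010 + 0.200) = 1.28 |
| 100 | 30 (30%) | 2.802 × √(0.010 + 0.033) = 0.58 |

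For reference, the week-12 comparison under the same assumptions and no dropout gives 2.802 × √(2/50) = 0.56 and 2.802 × √(2/100) = 0.40. The remnant at week 24 would be weaker and, more importantly, self-selected. It would not be the randomised control group.

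**The case against.** The strongest reply is that week 24 is not wholly without a comparator. Controls who cross over enter the treatment arm and would presumably follow its weekly questionnaires, so they could have scores at study week 24. A comparison by randomised arm would then be concurrent. This stands as far as it goes: what is missing is a *usual-care* comparator, and the count of 12 against 0 refers to usual-care assessments only. But that analysis asks whether starting at once is better than starting 12 weeks later. It does not test a null against usual care. The protocol also has no crossover table, so the schedule itself has to be inferred.

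Three further points have some force.
- The endpoint sentence in section 8.1 names no comparator, and device-arm change at week 24 is fully scheduled. That is true, but the null is the stated test of that endpoint, so leaving 24 weeks in one and not the other would keep the ambiguity.
- Secondary endpoint 2 is only reported, with no test or contrast, so its defect is smaller: an undefined time origin, with an observation-arm value at 24 weeks that is not a usual-care value.
- This is a Phase II trial and a valid randomised test exists at week 12. That limits the damage, but it does not make the 24-week part testable.

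The gap cannot be left to an analysis plan. A plan can choose a model, but it cannot supply usual-care observations that the protocol does not collect.

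**Conclusion.** The concern holds. The 24-week part of the primary null has no usual-care data scheduled behind it: 0 of 50 to 100 controls, with week 12 the last assessment shared by the two arms. This follows from the text and schedules and does not depend on how many controls cross over. It assumes only that the single control table in section 4.1 is the complete usual-care schedule, and no other section adds to it.

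The week-12 comparison is sound and untouched. The point must still be corrected because it lies in the primary effectiveness hypothesis and, as worded, lets an uncontrolled or differently controlled week-24 result stand as a primary finding against usual care.

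**What to change.** 1. **Section 8.1.** Limit the between-arm null, and the effectiveness endpoint that it tests, to change from baseline to week 12 by randomised arm.
2. **Week-24 data.** Report them descriptively, either within arm or labelled as immediate against delayed device start, with no claim against usual care.
3. **Section 8.2, secondary endpoint 2.** Either drop the 24-week figure for the observation arm, or define it as 24 weeks after device start in controls who crossed over and label it post-crossover data.

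The cost is wording in two sections, with no added patients or visits. The sponsor gives up a controlled 24-week claim that the design cannot support. The alternative is to schedule usual-care follow-up of controls to week 24. That adds visits and, while crossover is offered after week 12, would reach only the self-selected controls who decline it.
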